## **5.2 Assessment of Adverse Events.**

### **5.2.1 Definitions of Adverse Events.**

**Adverse Event.** An adverse event (AE) is defined as any untoward medical occurrence, including an exacerbation of a pre-existing condition, in a patient in a clinical investigation who received a pharmaceutical product. The event does not necessarily have to have a causal relationship with this treatment.

**Serious Adverse Event.** A serious adverse event (SAE) is defined as any AE which results in death, is immediately life-threatening, results in persistent or significant disability/incapacity, requires or prolongs patient hospitalization, is a congenital anomaly/birth defect, or is to be deemed serious for any other reason if it is an important medical event when based upon appropriate medical judgment which may jeopardize the patient and may require medical or surgical intervention to prevent one of the other outcomes listed in the above definitions.

**Intensity of Adverse Event.** The intensity of the AE should be judged based on the following:

1. Mild: the adverse event is temporary and easily tolerated by the subject;
2. Moderate: the adverse event causes the subject discomfort and interrupts the subject's normal activities.

3. Severe: the adverse event causes considerable interference with the subject's normal activities and may be incapacitating or life threatening including hospitalization or prolongation of hospitalization.

Causal Relationship of Adverse Event. Medical judgment should be used to determine the relationship, considering all relevant factors, including pattern of reaction, temporal relationship, de-challenge or re-challenge, confounding factors such as concomitant medication, concomitant disease and relevant history. Assessment of causal relationship should be recorded in the case report forms.

Yes: There is a reasonable causal relationship between the product administered and the AE.

No: There is no reasonable causal relationship between the product administered and the AE.

Worsening of the underlying disease or other pre-existing conditions will be recorded as an (S)AE in the CRF.

Changes in vital signs, ECG, physical examination and laboratory test results will be recorded as an (S)AE in CRF, if they are judged clinically relevant by the investigator.

**5.2.2 Adverse Event Reporting.** Investigators will report AEs using standardized event, resolution and association codes. The SAE reporting period includes the entire study duration (1 month) and an additional three days. All acute coronary syndromes (ACS) will be reported.

The Principal Investigator shall forward all (1) SAEs and non-serious AEs relevant to the reported SAE and (2) non-serious AEs which are assessed as related to the study drug by [contact]) to the BI Safety Contact Point ([name]).

For forwarding SAEs, any non-serious AE relevant to the reported SAE, and all related non-serious AEs, the Principal Investigator shall use the study specific non-interventional study AE report form.

All reports concerning SAEs and any non-serious AEs relevant to the reported SAE, and any related non-serious AEs shall be forwarded to the BI Safety Contact Point immediately (within twenty four hours or next business day whichever is shorter).

The Principal Investigator shall be responsible to follow up on all information regarding a reported Drug Exposure during Pregnancy. Principal Investigator shall ensure that any SAE / related AE during and after pregnancy will be reported to the BI Safety Contact Point on the study specific non-interventional study AE report form and the timeline described above.

The AE reporting process is further described in the Safety Data Exchange Agreement.

### **5.2.3 Assessment of safety laboratory parameters.**

**Imaging Data Collection.** No additional imaging will be required for study participants. Only standard clinical data will be collected. Acute baseline CT scans will be collected. Dicom files will be transferred to a central imaging database. All patients will have a follow-up non-contrast CT scan  $7\pm 2$  days after enrolment, in order to assess for early asymptomatic hemorrhagic transformation. In the event of any clinical deterioration, a repeat CT scan will be performed immediately. In addition, any supplemental brain imaging completed within the first 30 days after enrolment will be collected.

**Image Analysis.** Dicom CT data will be transferred to the Stroke Imaging Laboratory at the University of Alberta for post-processing and analysis. All image assessments will be performed using software developed specifically for CT brain image analysis (Quantomo software package, Cybertrial Inc, Calgary, AB). The extent of any objective acute and chronic ischemic changes on all CT scans will be

assessed using Alberta Stroke Program Early CT Scores (ASPECTS). It is expected baseline scans will not have evidence of acute ischemic changes, but this will be verified centrally. The extent of periventricular leukoariosis will also be measured using planimetric techniques and an intensity threshold algorithm included in the Quantomo software package.

All cases of hemorrhagic transformation seen on post-dabigatran treatment scans will be graded using the ECASS (European Cooperative Acute Stroke Study) hemorrhage classification scheme:

6. PH2 - parenchymal hemorrhage as a blood clot in more than 30% of the infarcted area with substantial space-occupying effect.
7. PH1 - parenchymal hemorrhage as blood clots in 30% or less of the infarcted area with some slight space-occupying effect.
8. HT2 - hemorrhagic transformation 2 - confluent petechiae within the infarcted area but no space-occupying effect.
9. HT1 - hemorrhagic transformation 1 – small petechiae along the margins of the infarct.
10. R - remote ICH, i.e. not topographically related to the infarct (most often in the contralateral hemisphere).

*A symptomatic ICH will be defined as PH2, associated with an NIHSS deterioration of  $\geq 4$  points.*

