## **4.0 Treatments**

**4.1 Prescribed Study Treatments.** Patients in whom dabigatran is initiated within 14 days of TIA/stroke symptom onset will be included in the registry. The timing of initiation of therapy within that 14 day window will be determined by the treating physician. The factors related to physician choice of initiation time (relative to symptom onset) will be recorded (**appendix 5**).

**4.1.1 Identity of test products and comparators.** NA.

**4.1.2 Treatment Group Assignment.** NA.

**4.1.3 Selection of Dose.** Patients will be treated either at a dose of 110 mg BID or 150 mg BID. The dose will be determined by treating physician. The physician rationale for the dose selected will be recorded in all cases (**appendix 6**).

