### **5.1.2 Secondary Outcomes.**

The rate of any objective hemorrhagic transformation on the day 7 post-dabigatran initiation non-contrast CT scan.

The rate of secondary hemorrhagic transformation in patients taking warfarin prior to the stroke/TIA.

The rate of hemorrhagic transformation in patients started on dabigatran within 7 days of stroke/TIA versus those started >7 days after symptom onset. Recurrent TIA/Ischemic Stroke within 30 days of dabigatran initiation.

Systemic hemorrhagic complication rate within 30 days of dabigatran initiation.

The rate of hemorrhagic transformation in patients started on dabigatran within 7 days of stroke/TIA versus those started >7 days after symptom onset.

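### The secondary imaging outcomes do not separate hemorrhagic transformation that arose before the first dabigatran dose from that which arose after it, and the untreated window varies with start time

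*Combined protocol and SAP*

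**What the plan says.** Section 4.1 sets the entry window: "Patients in whom dabigatran is initiated within 14 days of TIA/stroke symptom onset will be included in the registry". The treating physician chooses the day within it.

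Section 5.2.3 describes the imaging. At baseline, "Acute baseline CT scans will be collected", and "No additional imaging will be required for study participants". The baseline reading covers ischemic change and leukoaraiosis: "It is expected baseline scans will not have evidence of acute ischemic changes, but this will be verified centrally". HT grading is specified for later scans only: "All cases of hemorrhagic transformation seen on post-dabigatran treatment scans will be graded" on the ECASS scheme. The Synopsis (Imaging Parameters/Analysis) likewise ties grading to the day 7 scans.

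Section 5.1.2 (Secondary Outcomes) defines the imaging outcome as "The rate of any objective hemorrhagic transformation on the day 7 post-dabigatran initiation non-contrast CT scan" and lists the comparison of starts within 7 days of the event against later starts. The Synopsis (Statistical Analyses) repeats that comparison. Section 7.1 divides HT cases by all enrolled patients and makes time to initiation a stratum. Objective 2 in section 2.2 is the frequency of asymptomatic HT after 7 days of treatment. Appendix 4 tabulates asymptomatic HT by days since initiation.

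The follow-up CT has two anchors. Section 5.2.3 places it 7±2 "days after enrolment, in order to assess for early asymptomatic hemorrhagic transformation", and the Synopsis endpoint list also counts from enrolment. Section 5.1.2 and the Synopsis (Study Procedures) count from initiation or treatment.

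**The concern.** Objective 2 asks what happens after dabigatran is started. The outcome as defined measures whatever HT is visible on one CT, whenever it arose. A silent petechial change on day 4 in a patient first dosed on day 10 counts in the same way as one that appears on treatment.

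The untreated interval also lengthens with start day, which is the factor being compared. Part of any difference between early and late starters may therefore reflect time since stroke and not the drug. The rows of Appendix 4 cannot be filled reliably for silent HT if nobody records whether it was there before the first dose.

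**Working it through.** **The plan's own figure.** Section 2.3 expects symptomatic HT of 0.6%. From its inputs, 1.7% × 1/3 = 0.567%, or about 3 events in 500. This reproduces. It concerns the symptomatic outcome and is not in dispute. The plan gives no rate for silent HT off drug, and the Synopsis says the HT rate in this population has not been accurately documented.

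**Step 1: share of the interval that is untreated.** Take the baseline scan at onset (day 0), the first dose on day s and the follow-up CT on day s + 7. The pre-dose share is s/(s + 7):
- day 1: 1/8 = 12.5%
- day 7: 7/14 = 50%
- day 10: 10/17 = 59%
- day 14: 14/21 = 67%

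At day 14 the ±2 day window gives 14/23 = 61% to 14/19 = 74%. These are shares of time. They become shares of HT only if the hazard is constant, HT stays visible on CT, and nobody with HT is kept off treatment.

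**Step 2: effect on the timing comparison.** Assumptions, none from the documents: 5% off-drug HT over 14 days, no drug effect, early starters dosed on day 3 and late starters on day 11, CT 7 days after the dose. Under a constant hazard with lasting visibility:
- early: pre-dose 5% × 3/14 = 1.07%; post-dose 5% × 7/14 = 2.50%; total 3.57%
- late: pre-dose 5% × 11/14 = 3.93%; post-dose 2.50%; total 6.43%
- late minus early in pre-dose cases: +2.86 points (+1.14 at an assumed 2%, +5.71 at 10%)

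With 70% early starters, 500 × (0.7 × 1.07% + 0.3 × 3.93%) = 9.6 pre-dose cases would be reported alongside 500 × 2.50% = 12.5 post-dose cases.

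**Step 3: vary the assumptions, still at 5%.** The declining hazard has cumulative HT proportional to 1 − exp(−t/4), scaled to 5% by day 14. Fading weights a case arising on day u by 2^(−(T − u)/h), for a scan on day T and half-life h. Entries are percentages or percentage points; differences are from unrounded values.

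| Hazard | CT visibility | Early pre / post | Late pre / post | Late − early, pre-dose cases | Late − early, all HT seen |
|---|---|---|---|---|---|
| Constant | lasting | 1.07 / 2.50 | 3.93 / 2.50 | +2.86 | +2.86 |
| Constant | half-life 10 d | 0.60 / 1.98 | 1.69 / 1.98 | +1.10 | +1.10 |
| Constant | half-life 5 d | 0.33 / 1.60 | 0.76 / 1.60 | +0.43 | +0.43 |
| Declining | lasting | 2.72 / 2.01 | 4.83 / 0.27 | +2.11 | +0.37 |
| Declining | half-life 5 d | 0.82 / 1.12 | 0.67 / 0.15 | −0.15 | −1.12 |
| Week 1 only | lasting | 2.14 / 2.86 | 5.00 / 0.00 | +2.86 | 0.00 |

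In the first row, the difference in pre-dose cases falls to +1.43 if half of the patients with pre-dose HT never start dabigatran, and to 0 if none of them start.

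**Step 4: what counting only new HT would do.** Under a constant hazard with lasting visibility, both groups show 2.50% and the spurious difference disappears. Under a week-1-only hazard, early starters show 2.86% and late starters 0%, again with no drug effect. Neither count is neutral on its own.

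**The case against.** Four points can be made against the concern.

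A reader might infer that the primary safety rate is inflated. The documents do not support that. Section 5.1.2 (Primary Outcome) requires PH2 with NIHSS worsening of at least 4 points within 30 days of initiation, deterioration triggers an immediate CT, and section 6.1 provides central adjudication. Silent pre-dose HT does not qualify alone. What remains is an earlier PH2 paired with a later deterioration from another cause. The protection depends on the NIHSS condition, which the Synopsis (Statistical Analyses) leaves out when it names the primary outcome.

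A reader might also infer that late starters are made to look worse, for example that a day 10 start shows 17/8 = 2.1 times the HT of a day 1 start. That ratio needs a constant hazard, lasting visibility, no selection out of treatment and a scan anchored to the first dose. If natural HT were confined to the first week and stayed visible, both scans would show all of it and the ratio would be 1. Selection is plausible too: only treated patients are followed (section 3.3), and clinically significant intracranial hemorrhage and label contraindications are excluded.

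Nor should one conclude that pre-dose scans are unavailable. Section 5.2.3 names only the acute scan, the follow-up CT and a further category ("any supplemental brain imaging completed within the first 30 days after enrolment will be collected"), but the Synopsis says all neuro-imaging is collected and all standard-care imaging goes to the core laboratory.

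Finally, the study is descriptive and hypothesis generating (sections 7.1 and 7.2), and the Limitations concede selection before treatment and a link between severity and start time. This lowers the stakes of the comparison. It does not make objective 2 measure what it states, and the Limitations do not mention HT already present at the first dose.

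**Conclusion.** The gap is real for the secondary imaging outcomes: any HT and asymptomatic HT on the follow-up CT, and their comparison by start time. As written, untreated HT counts toward a frequency described as following treatment, and the opportunity for it differs with initiation day. The exclusions, the CT on deterioration and the adjudication do not separate silent pre-dose HT from post-dose HT.

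The untreated share of the interval runs from 12.5% (day 1 start) to 67% (day 14 start), provided the scan is 7 days after the first dose. The size and direction of the effect on the timing comparison cannot be fixed from the documents. At an assumed 5% off-drug rate, the late-minus-early difference in pre-dose cases runs from +2.86 to −0.15 points across the scenarios above. When the hazard is front-loaded, the pre-dose cases can instead hide a lower post-dose rate in late starters. The change is worth making because it alters the reported rate at little cost.

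**What to change.** 1. In section 5.2.3, apply the ECASS grading to the baseline scan and to every available pre-dose scan, and record the date of the last one. Align the collection wording with the Synopsis, which already covers all neuro-imaging.
2. In sections 5.1.2 (Secondary Outcomes) and 7.1, report HT on the follow-up CT in three categories: present before the first dose; new or of higher grade since the last pre-dose scan; and onset undetermined because no pre-dose scan falls within a pre-specified window. Use the second category for objective 2.
3. Present the comparison of starts within 7 days against later starts for any HT and for new HT side by side. Add a sensitivity analysis restricted to patients with a recent pre-dose scan. State, there and under Limitations, that time since onset, severity and selection confound the comparison either way.
4. Reconcile the anchor of the follow-up CT between enrolment and initiation. If enrolment precedes the first dose, a scan timed from enrolment covers a shorter treated period, and the shares in step 1 no longer apply.

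The cost is wording and extra reading of scans already taken; no additional imaging is required. There are two downsides. The restricted subset will be smaller and selected, since patients rescanned before dosing may have been rescanned for a reason. The new-HT comparison can also be unfavourable to early starters if natural HT is concentrated in the first week, which is why it should not replace the any-HT comparison.

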## **5. Variables and Assessment.**

**5.1.1 Effectiveness.** This is a registry of the safety of early anticoagulation (see 5.2). A measure of the effect of early anticoagulation will be assessed; the rate of new ischemic stroke/TIA occurrence within the 30-day study period will be recorded. It is recognized that the event rate will be low and the study is neither designed, nor powered to demonstrate a decrease in early ischemic stroke rates.

**5.1.2 Primary Outcome (Safety).** The primary study outcome measure is the symptomatic hemorrhagic transformation rate (PH2 associated with clinical deterioration, defined as worsening of NIHSS score of 4 or more points, within 30 days of initiating dabigatran therapy).

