## **6. Investigational Plan**

**6.1 Visit Schedule / Clinical Data Collection.** No additional procedures or assessments will be mandated for study participants. Standard clinical assessments and data will be collected. This will include baseline National Institutes of Health Stroke Scale NIHSS, Glasgow Coma Scale (GCS) and vital signs, which will be recorded in a case report form. Stroke risk factors, past medical history and medications, baseline complete blood count, coagulation profile and renal function tests will also be recorded. CHADS2 and CHADSVaSC scores will also be recorded. Clinical endpoints will be ischemic stroke or intracranial hemorrhage within 30 days of anticoagulant initiation. All cerebral ischemic and intracranial hemorrhagic endpoints will be centrally adjudicated from anonymized clinical records, with the intracranial hemorrhages classified as described above. A data collection form will be filled out for each subject at 30 days post-enrolment indicating clinical status and occurrence of outcome events.

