## **7. Statistical Methods and Sample Size**

**7.1 Statistical Analysis and Sample Size Considerations:** The registry will include 500 patients. This sample size is considered adequate to ensure inclusion of a significant number of patients treated at a range of time points within the post-stroke period. The primary analysis will be done on an Intention

To Treat basis. We will also complete a sensitivity analysis on individuals who discontinued dabigatran treatment and/or switched to other antithrombotic agents. Based on the inclusion/exclusion criteria, there will not be any individuals taking dabigatran concomitantly with other antithrombotic drugs.

The primary and secondary outcomes will be defined with descriptive statistics. The rate of PH2 (and all other forms of hemorrhagic transformation) will be defined as a ratio (%) of the total number of patients enrolled in the study (ITT analysis).

The primary stratification variable is warfarin use prior to the TIA/minor stroke. The secondary strata are 1. Dabigatran dose (150 mg BID versus 110 mg BID) and 2. Time to initiation of therapy (0-2 days, 3-7 days and > 7 days). All results including baseline patient characteristics will be stratified by use of warfarin prior to the event and by the dabigatran dose after the event as described in **appendices 2-4**.

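### The primary safety outcome counts only PH2, a grade that presupposes an infarct, so a symptomatic bleed in a patient with no infarct, or one graded R, is left out of the headline rate

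*Combined protocol and SAP*

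**What the plan says.** Section 5.1.2 (Primary Outcome) sets the endpoint: "The primary study outcome measure is the symptomatic hemorrhagic transformation rate (PH2 associated with clinical deterioration, defined as worsening of NIHSS score of 4". The required worsening is thus at least 4 points, and the window is 30 days from the first dabigatran dose. Section 5.2.3, like the Synopsis, grades bleeds on the ECASS scale. The top grade is "PH2 - parenchymal hemorrhage as a blood clot in more than 30% of the infarcted area with substantial space-occupying effect". The last grade is "R - remote ICH, i.e. not topographically related to the infarct (most often in the contralateral hemisphere"). The other three grades (PH1, HT2, HT1) also refer to the infarct. The section closes by restricting the symptomatic category to one grade: "A symptomatic ICH will be defined as PH2, associated with an NIHSS deterioration of" at least 4 points.

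Section 3.3.2 and the Synopsis admit TIA patients as well as minor strokes. Entry imaging, by CT or MRI, must fit an ischemic cause, but an infarct need not be shown.

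Section 6.1 makes intracranial hemorrhage within 30 days a clinical endpoint, adjudicated centrally, "with the intracranial hemorrhages classified as described above". That scale has no grade for subdural, subarachnoid or intraventricular blood. Under section 7.1 the rate of PH2, and of every other form of transformation, "will be defined as a ratio (%) of the total number of patients enrolled in the study".

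No section says how to grade a parenchymal bleed when no infarct is identified, or which scan defines the infarcted area.

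**The concern.** The Synopsis and section 3.1 say safety will be shown by a low hemorrhage rate. Section 3.2 takes its safety threshold from warfarin-associated intracranial hemorrhage (0.5 to 2.5 per 100 patient-years). Neither is limited to bleeding into an infarct, but the primary numerator is. A hematoma that worsens the NIHSS by 4 or more points matters to the patient and the prescriber whether or not an infarct lies beneath it. Under the current wording, its place in the headline figure depends on whether an infarct can be identified.

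The study has a single arm, so no comparator carries the same omission. About three primary events are expected, so one or two excluded bleeds would change the reported rate materially.

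**Working it through.** **Step 1: follow a symptomatic bleed through the definitions.** Take a parenchymal hematoma with NIHSS worsening of 4 or more points.

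- *Infarct identified, bleed within it.* The 30% test can be applied. If the bleed is PH2, it is a primary event.
- *Infarct identified, bleed elsewhere.* The grade is R. Symptomatic ICH is limited to PH2, so this is not a primary event.
- *No infarct on any scan.* The 30% test has no reference area, so neither PH grade can be assigned. R also presupposes an infarct. The bleed goes to R by default or to no grade, and is not a primary event.

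In all three cases the patient stays in the section 7.1 denominator.

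**Step 2: the plan's own figure.** Section 2.3 takes 1.7% for heparin and a relative rate of 1/3: 1.7% × 1/3 = 0.567%, which rounds to the stated 0.6%. On 500 patients that is 500 × 0.006 = 3.0 expected events. The sample size itself has no calculation to reproduce.

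**Step 3: size of the effect, as an illustration.** Let f be the share of patients with no infarct on any scan. The documents do not give f; I assume 0.25 to 0.75. I also assume that the true rate of symptomatic parenchymal bleeding is 0.6%, that risk is equal with and without an infarct, and that every bleed in a patient with an infarct is gradable as PH2. Then:

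- observed rate = 0.6% × (1 − f)
- expected events = 500 × observed rate
- P(no events) = (1 − observed rate)^500

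| f | Observed rate | Expected events | P(no events) |
|---|---|---|---|
| 0 | 0.60% | 3.0 | 4.9% |
| 0.25 | 0.45% | 2.25 | 10.5% |
| 0.50 | 0.30% | 1.5 | 22.3% |
| 0.75 | 0.15% | 0.75 | 47.2% |

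**Step 4: what zero events would mean.** The exact two-sided 95% upper limit for 0 of n is 1 − 0.025^(1/n). For n = 500 it is 0.74%, and this limits symptomatic PH2 only. If only 375, 250 or 125 patients could contribute a gradable bleed (f = 0.25, 0.50, 0.75), the same zero count leaves open a rate of up to 0.98%, 1.46% or 2.91%. This shows how much less a zero would establish; it is not a proposal to change the denominator.

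The illustration covers only no-infarct bleeds. Symptomatic R bleeds in patients with an infarct would add to the shortfall, but the documents give no figure for them.

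**The case against.** The strongest reply is that the outcome is symptomatic hemorrhagic *transformation*, which is tied to an infarct by concept. Counting other hematomas would make it a different outcome. That is a fair reason to keep symptomatic PH2 as defined, but not to leave the broader rate unreported when the stated aim and threshold are broader.

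A reader might infer more than the documents support:

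- *That TIA patients cannot have the event.* Section 5.2.3 does say "It is expected baseline scans will not have evidence of acute ischemic changes", but that concerns baseline scans. Grading uses post-treatment scans: the day 7 CT, a CT at any deterioration, and other imaging to 30 days. An infarct absent at baseline may show there. Section 1.1 describes TIA and minor stroke as a continuum and reports new MRI infarction within 7 days in 18% of patients. Someone without an infarct at entry can still have one and bleed into it.
- *That such bleeds vanish from the study.* The Synopsis (Statistical Analyses) lists any intracerebral hemorrhage as a secondary outcome, section 6.1 adjudicates intracranial hemorrhage, and the DSMB receives all parenchymal hemorrhage cases. However, that secondary outcome is absent from the Synopsis endpoint list and from section 5.1.2, and Appendix 4 has no row for symptomatic bleeds outside transformation.
- *That the denominator should be patients with an infarct on any scan.* This would select on post-treatment findings, including recurrent infarcts. All treated patients is the right base for risk in the target population.
- *That a bleed meeting either PH2 criterion should count as PH2.* PH1 is "PH1 - parenchymal hemorrhage as blood clots in 30% or less of the infarcted area with some slight space-occupying effect", so a clot filling more than 30% of a small infarct with only slight mass effect fits neither PH grade as printed. The documents give no basis for choosing a tie rule, and reporting symptomatic bleeds of every grade makes one unnecessary.

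It is also true that the study is descriptive and, by section 7.2, hypothesis generating only, so no formal test depends on the figure.

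**Conclusion.** The point holds as a gap in the outcome definition. Applied literally, the primary rate omits symptomatic parenchymal bleeds in patients with no infarct on any scan, and symptomatic R bleeds, while those patients remain in the denominator. The direction is downward relative to the stated aim and threshold.

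The size cannot be fixed from the documents. Under the assumed 25% to 75% without an infarct and equal bleed risk, 0.6% would be seen as 0.45% to 0.15%. If infarct-free patients bleed less often than others, the loss is smaller. The conclusion does not extend to saying that these patients are free of risk for the event or that their bleeds go unrecorded. This is an inexpensive improvement to make before adjudication begins.

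**What to change.** 1. In section 5.2.3 and the Synopsis imaging entry, add a grade for parenchymal hemorrhage with no identifiable infarct, and state which scan or scans define the infarcted area.
2. In section 5.1.2, section 7.1 and Appendix 4, add the rate of symptomatic intracranial hemorrhage of any grade (PH1, PH2, R, no-infarct, other intracranial) with NIHSS worsening of 4 or more points. Report it beside symptomatic PH2, on all treated patients (section 3.3 follows only these), with exact 95% confidence intervals.
3. Describe both rates by presence or absence of an infarct on pre-treatment imaging. This avoids selecting on findings that arise after treatment.

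The cost is some wording and a few more fields for the central imaging laboratory; no new scans are needed. The downside for the sponsor is that the reported hemorrhage rate may be slightly higher.
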